#### **9.4.6. Other Analyses**

Subgroup Analyses A prespecified list of subgroups will be identified in the SAP. The treatment effect within each subgroup will be summarized. Other subgroup analyses not specified in the SAP may be performed as deemed appropriate. These subgroups will be based on important characteristics, for example, prognostic significance.

##### **9.4.6.1. Biomarker Analyses**

Single-marker and/or multi-marker statistical analysis may be performed to explore the association between biomarkers, dose/exposure, and clinical outcomes. For an example, an association analysis between CD73 expression and clinical benefit may be triggered after data in Phase 1b Cohort C is collected.

### **9.5. Interim Analyses**

In the Phase 1a portion of this study, dose-escalation data (monotherapy and combination) will be reviewed for safety on a cohort-by-cohort basis, until the MTDs (or the highest DLs if MTDs are not reached) are determined for each treatment part. The purpose of these cohort-by-cohort reviews is to evaluate the safety data at each DL and determine if a DLT has been observed that would suggest MTD has been met or exceeded. The investigators and the Lilly study team will make the determination regarding dose escalation based upon their review of the safety and tolerability data as described in this protocol.

In the Phase 1b portion of this study, a safety review will be performed after the first 20 patients across all dose-expansion cohorts are enrolled and treated for 1 cycle, and then every 6 months afterward. For preliminary efficacy evaluations, the following interim analyses are planned:

- Cohort C (patients with CD73+ tumors) and Cohort D (castrate resistant prostate cancer): for each cohort, an interim analysis of safety and efficacy is planned after 10 patients in the monotherapy arm are treated and completed 2 cycles or have discontinued before the first postbaseline tumor assessment. Per 2:1 randomization ratio, at this interim analysis approximately 20 patients in the combination arm are treated. Preliminary efficacy will be evaluated on these 20 patients in the combination arm and on these 10 patients in the monotherapy arm, and the combination arm may be expanded with additional 20 patients if the totality of efficacy, safety, and PK/pharmacodynamics data warrant expansion. If no objective responses are observed, both as monotherapy or combination therapy, the combination arm(s) will not continue enrollment.
- Cohort E (TNBC): an interim of safety and efficacy is planned after approximately 20 patients are treated and completed 2 cycles or have discontinued before the first postbaseline tumor assessment. The trial may continue to enroll 20 additional patients for the final analysis if the totality of efficacy, safety, and PK/pharmacodynamics data supports the addition of patients. If no objective responses are observed, additional patient enrollment to Cohort E will be terminated.

The interim analyses may be combined if they are expected to occur within a similar timeframe; interim analyses may also be combined with any prespecified safety review or annual reporting (such as an update to the IB or Development Safety Update Review, etc.).

If it is deemed that enough data are obtained to assess the primary objective and the secondary objectives, a CSR might be created before the last patient visit. In this case, all data until the data-cutoff date will be used for the analysis of safety, efficacy, PK, and pharmacodynamic biomarkers. All data defined in the protocol will continue to be collected from patients on treatment after the data-cutoff date. These data may be reported separately and the analyses on all patients including these data may not be performed.

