Tumor markers	X		See Instructions											Collect tumor markers only for corresponding to cancer type: PSA- Prostate For mCRPC patients with nonmeasurable disease, PSA should be collected every 3 weeks (for the first 12 weeks of therapy) and evaluated every 9 weeks for progression after the first evaluation period (at 12 weeks). See Section 8.1.3 and Appendix 2 for further details.  CEA - Pancreatic CA-125 - Ovarian CA 19-9 - Pancreatic For other indications please collect relevant tumor markers (e.g., CA 19-9) Q6W

Baseline, On-Study and Post-Study Treatment Follow-up SoA														
	Baseline		Cycle = 21 days							Short-Term Follow Up a			Long-Term Follow-Up b	Instructions
	(Day Relative to C1D1)		Cycle 1				Cycle 2		Cycle 3-n	801	802	803	804-X	
			(±3 days)				(±3 days)		(±3 days)	30 day follow-up ±5 days	60 day follow-up ±5 days	90 day follow-up ±5 days	Q90D	
Procedure	≤28	≤7	D1	D2	D8	D15	D1	D2	D1					
														throughout the study (C1D1, C3D1, etc.). See Appendix 2.
Pregnancy test	X	≤24h	See Instructions							X	X	X		Applies only to women of childbearing potential. See Section 8.3.4. for pembrolizumab-specific requirements and Appendix 2. Pregnancy test required at monthly intervals during study treatment in both treatment arms and up to 120 days after study treatment discontinuation for patients receiving LY3475070 and pembrolizumab and at 7 days after study treatment discontinuation for patients receiving LY3475070 monotherapy per Section 8.3.4.
Tumor assessment-radiological imaging	X		See Instructions							See Instructions				Perform locally according to RECIST 1.1, using the same imaging method (e.g., CT or MRI) at each assessment every 9 weeks ± 7 days for the first year and every 12 weeks (±7 days) thereafter until a discontinuation criteria is met.
Radionuclide bone scan	X		See Instructions							See Instructions				Disease progression should be confirmed per iRECIST by the site 4 to 8 weeks after site-assessed first radiologic evidence of PD in clinically stable participants. Participants, who have unconfirmed disease progression may continue on treatment at the discretion of the investigator until progression is confirmed by the site. Note: Imaging must be performed within 28 days before C1D1. See Section 8.1

Baseline, On-Study and Post-Study Treatment Follow-up SoA														
	Baseline		Cycle = 21 days							Short-Term Follow Up a			Long-Term Follow-Up b	Instructions

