## Cohort E: Patients with mTNBC

- g) Prior PD-1/L1 inhibitor therapy allowed;
- h) Patients must have received treatment for metastatic disease (at least 1 regimen of cytotoxic chemotherapy for metastatic disease);

Participants are eligible to be included in the study only if **all** of the following criteria apply:

8. Must be able to provide informed consent, as described in Appendix 1, which includes compliance with the requirements and restrictions listed in the informed consent form (ICF) and in this protocol, according to local regulations and are at least 18 years of age.
9. Men with partners of childbearing potential must use a condom during intercourse. Men with partners of childbearing potential or women with childbearing potential must agree to use 2 effective methods of contraception including a highly effective contraceptive method of birth control (Appendix 3) during study treatment and for at least 120 days following the last dose of LY3475070 and pembrolizumab or country requirements, whichever is longer. For patients receiving LY3475070 only, contraception should be maintained for 7 days following the last dose. Additional guidance for contraception during and after study intervention are located in Appendix 3.
10. Women of childbearing potential must have a negative urine pregnancy test at the screening visit followed by a negative serum pregnancy test documented within 24 hours prior to initiation of treatment. If the screening urine test is positive or cannot be confirmed as negative, a serum pregnancy test will be required. Additional guidance for pregnancy testing during and after study intervention is located in Appendix 2 and Appendix 3.
11. Have at least 1 measurable lesion using standard techniques by RECIST version 1.1 (Eisenhauer et al. 2009). **Exception:** patients enrolled in the dose escalation phase and mCRPC patients enrolled in Cohort D1 and D2 are **not** required to have measurable disease.
12. Have a performance status (PS) of 0 or 1 on the Eastern Cooperative Oncology Group (ECOG) scale (Oken et al. 1982).
13. Previous treatments: Have discontinued all previous treatments for cancer and recovered from the acute effects of therapy (except alopecia). Patients must have discontinued from previous treatments, as shown below:

Previous Treatment	Length of Time Prior to First Dose of LY3475070
Endocrine therapies	$\geq 14$ days

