### 8.1. Efficacy Assessments

#### 8.1.1. RECIST V1.1 for Tumor Response Assessment

Please follow the guidelines below when assessing tumor response:

- Response Evaluation Criteria in Solid Tumors (RECIST) v1.1 will be applied as the primary criteria for assessment of tumor response (Eisenhauer et al. 2009).
- The extent of computed tomography (CT) or magnetic resonance imaging needed to establish baseline tumor burden is based upon the investigator's determination.
- Tumor assessments will be performed for each patient at the times shown in the SoA (Section 1.3). Counting from C1D1, for the first year of study treatment, disease status should be evaluated radiologically per RECIST v1.1 guidelines every 9 weeks ( $\pm 7$  days) for the first year, and every 12 weeks ( $\pm 7$  days) thereafter (until a discontinuation criterion is met).
- Perform assessments as scheduled, even if study treatment is delayed or omitted, except when deemed not feasible in the opinion of the investigator because of the patient's clinical status.
- Standard of care scan (pre-ICF) may be used as baseline provided it meets technical requirements for inclusion criteria and occurred within 28 days of treatment.

Per RECIST v1.1 imaging guidelines:

- imaging modality (e.g., CT or magnetic resonance imaging [MRI]) obtained for the study baseline should be repeated throughout the study as described in SoA;
- Intravenous and oral contrast should be used as clinically indicated;
- While CT imaging with slices  $\leq 5$  mm, MRI imaging is also acceptable;

- CT images from positron emission tomography-CT scans may be used for response assessment if the associated CT scan has the same quality as a diagnostic CT.

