6.9.1. Extent of Exposure

LY3475070 will be administered PO QD on a 28-day cycle until PD, unacceptable toxicity or other criterion for study discontinuation is met. In the absence of PD, unacceptable toxicity or other criterion for study discontinuation is met, pembrolizumab may be administered for a maximum duration of 24 months (35 cycles).

Pembrolizumab will be administered IV 200mg Q3W in cohorts B, C1, D1 and E.

The actual cumulative dose taken of LY3475070 will be derived from the difference between the total number of tablets/capsules dispensed and returned over the course of the patient's treatment taking into account the dose strengths.

The duration of therapy for the QD schedule will be calculated as last dose date-first dose date+1.

A summary of exposure will be provided for each study drug, including cycle received, cumulative dose, and duration of therapy.

A summary of dose intensity will be provided for each study drug. Dose intensity (per day) is calculated as total actual dose taken/duration of therapy (day). Relative dose intensity is calculated as $100 \times (\text{actual dose intensity per day}/\text{planned dose intensity per day})$.

Note that planned dose is the same as actual dose if there is no dose modification or cycle delays.

A summary of dose adjustments will be provided for each study drug, including dose omissions, dose reductions, cycle delays, and the corresponding reasons for dose adjustment.

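### The Phase 1b efficacy interims can trigger 14 to 28 days before the latest patients' first scheduled scan, yet a mandatory zero-response rule is applied at them

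*Protocol*

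**What the plan says.** **Trigger.** Protocol 9.5 states for each of Cohorts C and D that "an interim analysis of safety and efficacy is planned after 10 patients in the monotherapy arm are treated and completed 2 cycles". A patient who stops before the first post-baseline tumour assessment also satisfies the condition. Cohort E has the same condition, applied to about 20 patients. For the combination arms of C and D the text is looser: "Per 2:1 randomization ratio, at this interim analysis approximately 20 patients in the combination arm are treated". Those patients need not have completed any number of cycles.

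**Rule.** Adding 20 patients is a judgement on all the data, but the zero-response sentences leave no discretion. For C and D: "If no objective responses are observed, both as monotherapy or combination therapy, the combination arm(s) will not continue enrollment". For E: "If no objective responses are observed, additional patient enrollment to Cohort E will be terminated".

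**Schedule.** Protocol 1.3 sets a 21-day cycle, and Protocol 6.1 also refers to a 3-week cycle. Imaging in Protocol 1.3 is "at each assessment every 9 weeks ± 7 days for the first year". Protocol 8.1.1 fixes the origin: "Counting from C1D1, for the first year of study treatment, disease status should be evaluated radiologically per RECIST v1.1 guidelines every 9 weeks".

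**SAP.** Section 6.12 repeats the two-cycle trigger but has no zero-response stop. Section 6.9.1 gives a different cycle length: "LY3475070 will be administered PO QD on a 28-day cycle".

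**Cohort D.** Under Protocol 5.1, criterion 11, "patients enrolled in the dose escalation phase and mCRPC patients enrolled in Cohort D1 and D2 are not required to have measurable disease". Protocol 8.1.3 assesses response in patients without measurable disease by PSA, first evaluated at 12 weeks.

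**The concern.** The trigger counts cycles, while responses are seen at scans, and on the Protocol's calendar the two do not line up. A patient who has just completed two cycles has had no scheduled scan and cannot yet have shown a radiological response at a planned visit. Nothing in 9.5 makes the analysis wait for that scan.

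The discontinuation clause suggests the authors took two cycles to be the time of the first assessment, since it makes sense only if continuing patients have reached that assessment. This nearly fits the SAP's 28-day cycle, but not the Protocol's 21-day cycle.

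At stake is the chance of ending enrolment to an active regimen because no response has been seen yet. As written, that chance depends partly on accrual speed and on an unspecified data cut-off, not only on the drug.

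**Working it through.** **The plan's own numbers.** At 2:1, 10 monotherapy patients imply 2 × 10 = 20 combination patients, as stated. The caps add up: 10 + 20 + 20 = 50 in C and in D, 20 + 20 = 40 in E, 140 in total. The Clopper-Pearson upper limit for 0/20 recomputes to 0.168, matching the printed 0.17.

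**Timing.**
- 21-day cycle: 2 × 21 = Day 42. First scan at Day 63, window 56 to 70. Gap 14 to 28 days, nominally 21.
- 28-day cycle (SAP 6.9.1): 2 × 28 = Day 56. Gap 0 to 14 days, nominally 7.

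Visit windows and the 7-day delays allowed in Protocol 6.1 can shift these dates.

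**Effect in Cohort E.** The documents give no accrual rate, target response rate or error rate for this rule. Assumptions: uniform accrual of *r* patients per week, scan at Week 9, response visible at the first scan, unconfirmed responses counted, and a data cut on the trigger day. Patient *i* of 20 then has 6 + (20 − *i*)/*r* weeks of follow-up. Let *k* be the number with at least 9 weeks. P(zero responses) = (1 − ORR)^*k*, against (1 − ORR)^20 if all are scanned, which is 0.8^20 = 1.2% and 0.9^20 = 12%.

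| Accrual per week | 0.25 | 0.5 | 1 | 2 | 3 |
|---|---|---|---|---|---|
| Scanned (*k* of 20) | 19 | 18 | 17 | 14 | 11 |
| P(zero), ORR 20% | 1.4% | 1.8% | 2.3% | 4.4% | 8.6% |
| P(zero), ORR 10% | 14% | 15% | 17% | 23% | 31% |
| Scanned, cut 2 weeks later | 19 | 19 | 19 | 18 | 17 |
| Places left under the cap of 40 at Day 42 if enrolment continues, 20 − 6*r* | 18–19 | 17 | 14 | 8 | 2 |

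With the cut 2 weeks later, P(zero) at ORR 20% is 1.4 / 1.4 / 1.4 / 1.8 / 2.3%. A nominal 28-day cycle with no lag gives the same figures. With the cut 3 weeks later all 20 reach Week 9 and there is no excess. Scan timing also matters: at 2 per week and ORR 20%, P(zero) runs from 0.8^16 = 2.8% (scan at Week 8) to 0.8^12 = 6.9% (Week 10).

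**Cohort C.** This case needs a further assumption that 9.5 does not guarantee: all 30 patients have at least 6 weeks of follow-up.
- ORR 10% in both arms: *k* = 29 / 28 / 27 / 24 / 21 of 30. P(zero) = 0.9^*k* = 4.7 / 5.2 / 5.8 / 8.0 / 10.9%, against 0.9^30 = 4.2%.
- ORR 0% on monotherapy and 10% on combination, with every third patient on monotherapy: 20 / 19 / 18 / 16 / 14 combination patients scanned. P(zero) = 12.2 / 13.5 / 15.0 / 18.5 / 22.9%, against 12.2%.

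**Cohort D.** No figure is possible, because the share with non-measurable disease is unknown. For those patients the 12-week PSA evaluation (Day 84) falls 84 − 42 = 42 days after the trigger.

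**The case against.** Several points on the other side stand.

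- Day 42 is the earliest time, not a fixed date. Protocol 9.5 also lets interims be combined with each other or with safety and annual reporting. A lag of two weeks removes most of the excess, and three weeks removes all of it. The plan permits such a lag but does not require it.
- At 1 patient per week or slower the excess is modest. At ORR 10% most of the risk comes from having 20 patients, not from timing.
- The size of the loss depends on whether enrolment pauses, which 9.5 does not say. If it pauses, a full 20 patients can be withheld. If it does not, only about 2 places remain at 3 per week, so little is left to lose where the excess probability is largest.
- No formal test of response rate is planned (Protocol 9.1).

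A reader might infer more than the text supports. The interim is not an analysis without scans, because patients enrolled earlier will have had theirs. The plan does not say that unscanned patients are counted as non-responders: the all-treated denominator in Protocol 9.4.3.1 defines ORR, and the zero-response rule has no stated denominator. The rule ends enrolment, not treatment. The missing stop in SAP 6.12 need not be a disagreement over design, since the SAP is version 1, based on amendment (a).

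**Conclusion.** The mismatch is real and follows from the Protocol's own dates. A mandatory zero-response rule can be applied when the most recent patients have had no scheduled opportunity to show a radiological response.

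The dates are certain on the 21-day cycle; the consequence is conditional. It rests on assumed accrual, assumed response rates and a data cut on the trigger day. It is clearest in Cohort E, which has a single arm of about 20. It is smaller in C and D, where the natural reading needs zero responses in both arms, although their combination patients need only have been treated.

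This should be corrected because the repair is simple and appears to match what the authors intended. It does not make the design unsound.

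**What to change.** **Main change.** In Protocol 9.5 and SAP 6.12, replace the two-cycle condition with having had the first scheduled post-baseline tumour assessment (Week 9 ± 7 days). Keep the existing alternative of discontinuing before it. Apply this to every counted patient: both arms of C and D, and Cohort E. The trigger then no longer depends on cycle length. The 21-day cycle in Protocol 1.3 and the 28-day cycle in SAP 6.9.1 must still be reconciled.

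**Secondary clarifications.** State whether unconfirmed responses count for the zero-response rule; Protocol 9.4.3.2 requires two determinations for a best response of CR or PR, and 9.5 is silent. State whether PSA responses count in mCRPC patients with non-measurable disease, and when those patients are evaluable. Align SAP 6.12 with the Protocol's stop.

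**Cost.** Wording in two sections. Each interim moves about 3 to 4 weeks later on the 21-day cycle, or 1 to 2 weeks on the 28-day reading. If enrolment is held, no extra patients enter. If not, *r* × 3 to 4 weeks gives about 1–2 extra patients before the decision at 0.25 to 0.5 per week, 3–4 at 1 per week and 6–8 at 2 per week. At 3 per week the caps (40 in E, 50 in C and in D) limit it to about 2. Maximum cohort sizes do not change.

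**Limit.** Responses that first appear after Week 9, which Protocol 8.1.2 recognises as possible, would still be missed.

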## **10. Supporting Documentation and Operational Considerations**

### **10.1. Appendix 1: Regulatory, Ethical, and Study Oversight Considerations**

#### **10.1.1. Regulatory and Ethical Considerations**

- This study will be conducted in accordance with the protocol and with the following:
- Consensus ethical principles derived from international guidelines including the Declaration of Helsinki and Council for International Organizations of Medical Sciences (CIOMS) International Ethical Guidelines
- Applicable ICH Good Clinical Practice (GCP) Guidelines
- Applicable laws and regulations
- The protocol, protocol amendments, ICF, IB, and other relevant documents (e.g., advertisements) must be submitted to an IRB/IEC by the investigator and reviewed and approved by the IRB/IEC before the study is initiated.
- Any amendments to the protocol will require IRB/IEC approval before implementation of changes made to the study design, except for changes necessary to eliminate an immediate hazard to study participants.
- The investigator will be responsible for the following:
  - Providing written summaries of the status of the study to the IRB/IEC annually or more frequently in accordance with the requirements, policies, and procedures established by the IRB/IEC
  - Notifying the IRB/IEC of SAEs or other significant safety findings as required by IRB/IEC procedures
  - Providing oversight of the conduct of the study at the site and adherence to requirements of 21 CFR, ICH guidelines, the IRB/IEC, European regulation 536/2014 for clinical studies (if applicable), and all other applicable local regulations

After reading the protocol, each principal investigator will sign the protocol signature page and send a copy of the signed page to a Lilly representative.

The CSR coordinating investigator will sign the final CSR for this study, indicating agreement that, to the best of his or her knowledge, the report accurately describes the conduct and results of the study.

#### **10.1.2. Informed Consent Process**

- The investigator or his/her representative will explain the nature of the study, including the risks and benefits, to the participant or his/her legally authorized representative and answer all questions regarding the study.
- Participants must be informed that their participation is voluntary. Participants or their legally authorized representative will be required to sign a statement of informed consent that meets the requirements of 21 CFR 50, local regulations, ICH guidelines, Health Insurance Portability and Accountability Act (HIPAA) requirements, where applicable, and the IRB/IEC or study center.

- The medical record must include a statement that written informed consent was obtained before the participant was entered in the study and the date the written consent was obtained. The authorized person obtaining the informed consent must also sign the ICF.
- Participants must be re-consented to the most current version of the ICF(s) during their participation in the study.
- Participants otherwise eligible for Phase 1b Cohort C will sign the Cohort C informed consent prior to collection of the fresh tissue sample for determination of CD73 expression and potentially retained for biomarker testing.
- A copy of the ICF(s) must be provided to the participant or the participant's legally authorized representative and is kept on file.

Participants who are rescreened are required to sign a new ICF.

The ICF will contain a separate section that addresses the use of remaining mandatory samples for optional exploratory research. The investigator or authorized designee will explain to each participant the objectives of the exploratory research. Participants will be told that they are free to refuse to participate and may withdraw their consent at any time and for any reason during the storage period. A separate signature will be required to document a participant's agreement to allow any remaining specimens to be used for exploratory research. Participants who decline to participate in this optional research will not provide this separate signature.

